On Day 1, subjects will be randomized to one of three sequence groups (ABC, BCA, CAB, where A = VLN cigarette, B=subject's own-brand cigarette; and C= nicotine polacrilex gum), with approximately the same number of subjects per sequence group. On Day 4, subjects will be re-randomized into one of three sequence groups (ABC, BCA, CAB; randomization sequence for Part B will be different than that of Part A for each subject), with approximately the same number of subjects per sequence group.	On Day 1, subjects will be randomized to one of three sequence groups (ABC, BCA, CAB, where A = VLN cigarette, B=subject's own-brand cigarette; and C= nicotine polacrilex gum), with approximately the same number of subjects per sequence group. On Day 4, subjects will be re-randomized into one of three sequence groups (ABC, BCA, CAB), with approximately the same number of subjects per sequence group.	Minor clarification.
Section 10.3.4 Urine Drug Screen and Alcohol Testing Other section affected by this change: None		

CONFIDENTIAL

This protocol is the property of 22nd Century Group, Inc. and is intended solely for the guidance of the clinical investigation. This protocol may not—in full or part—be passed on, reproduced, published, or distributed to any person or entity who is not bound by written confidentiality agreement, for any purpose, without the prior consent of 22nd Century Group, Inc..

Original text with changes shown (strike through)	New wording (bolded text)	Reason/Justification for change
Urine drug screens will test for the following drugs of abuse: tetrahydrocannabinol (THC), opioids, amphetamines, cocaine, and benzodiazepines. The opioid panel will include codeine, hydrocodone, hydromorphone, levorphanol, oxycodone, oxymorphone, ranitidine	Urine drug screens will test for the following drugs of abuse: tetrahydrocannabinol (THC), opioids, amphetamines, cocaine, and benzodiazepines. The opioid panel will include morphine, codeine, heroin, hydrocodone, hydromorphone, and oxycodone.	Minor clarification based on modified opioid panel.
Appendix 17.1. Other section affected by this change: None		
\sim volume per sample (mL) 3 mL Part B 270 [90] 270 Total 270 296.5	\sim volume per sample (mL) 4 mL Part B 360 [90] 360 Total 360 386.5	Increase to per sample blood volume requirement as per bioanalytical lab.

CONFIDENTIAL

This protocol is the property of 22nd Century Group, Inc. and is intended solely for the guidance of the clinical investigation. This protocol may not—in full or part—be passed on, reproduced, published, or distributed to any person or entity who is not bound by written confidentiality agreement, for any purpose, without the prior consent of 22nd Century Group, Inc..

2. PROTOCOL SYNOPSIS

Name of Sponsor/Company: 22nd Century Group Inc.	
Name of Finished Product: Very Low Nicotine (VLN) cigarettes (0.4 mg nicotine/gram of tobacco)	
Study Title: Evaluation of the Abuse Liability of Very Low Nicotine (VLN) Cigarettes with Characterization of Nicotine Exposure Profiles in Adult Smokers	
Principal Investigator: [name]	
Study Center: Vince & Associates Clinical Research, Inc. [name]	
Study Period: Estimated date first subject enrolled: TBD Estimated date last subject completed:	Phase of Development: I
Objectives: The primary objective of the study is: 
• To evaluate the abuse liability of VLN cigarettes (0.4 mg nicotine/gram of tobacco) relative to own-brand cigarettes and 4 mg nicotine polacrilex gum under controlled use and uncontrolled (ad libitum) use conditions. The secondary objectives of the study are: 
• To compare the nicotine pharmacokinetic (PK) profiles of VLN cigarettes relative to own-brand cigarettes and nicotine polacrilex gum under controlled use and uncontrolled use conditions.• To characterize product use behavior of VLN cigarettes, own-brand cigarettes, and nicotine polacrilex gum.	
Methodology: This study will be a randomized, two-part, 3-way crossover designed to evaluate the abuse liability, PK, and product use behavior associated with study products, including VLN cigarettes, subjects' own-brand cigarettes, and nicotine polacrilex gum in healthy adult male and female exclusive smokers. Subjects will participate in a standard Screening visit and one 7-day Confined Assessment Phase, which will include a product trial session (Day -1), and two study parts (Part A and Part B). Following the Screening visit, eligible subjects will check-in to the study site on Day -1. Following the polacrilex gum training session, subjects will be required to abstain from nicotine- and tobacco-containing products for approximately 20 hours until the first product use session on Days 1 to 3; use of other nicotine-containing products will be prohibited throughout the study. No additional tobacco or nicotine products will be provided after the second product use on Days 4 to 6.	


Name of Sponsor/Company: 22nd Century Group Inc.
 
Name of Finished Product: Very Low Nicotine (VLN) cigarettes (0.4 mg nicotine/gram of tobacco)
 
On Day 1, subjects will be randomized to one of three product sequence groups in Part A, which will consist of an ad libitum product use session for each of the following study products for 4 hours in a randomized crossover manner (Days 1 to 3; one product per day):
 
▪ Product A: Non-menthol VLN cigarette▪ Product B: Own-brand non-menthol filtered standard king size cigarette▪ Product C: 4 mg Nicotine polacrilex gum (Nicorette® Original Flavor™) 
A pharmacodynamic measure (“use product again” visual analog scale [VAS]) will be administered at the end of each ad libitum product use period. Product use behaviors (i.e., number of units consumed, duration of gum in mouth) will be collected throughout each ad libitum product use period.
 
Upon completion of Part A, subjects will be randomized to one of three product sequence groups in Part B, which will consist of 3 study days (Days 4 to 6), with one product per day. Each study day will consist of: 1) Controlled Product Use Session (10 puffs from their own-brand cigarette or VLN cigarette [maximum 3 ± 2 seconds per puff] at approximately 30 ± 5-second interpuff intervals, or chew the nicotine polacrilex gum using the “chew and park” method for 10 minutes); and 2) Uncontrolled Product Use Session (ad libitum use for 10 minutes). The Controlled Product Use Session and Uncontrolled Product Use Session will be separated by approximately 6 hours. During Part B, pharmacodynamic measures, PK, and product use behavior (Uncontrolled only) will be collected at various time points each day (See Table 1).
 
Safety assessments including adverse events (AEs), physical examinations, vital signs (respiratory rate, pulse rate, blood pressure, and oral temperature), electrocardiogram (ECG), clinical laboratory tests (clinical chemistry, hematology, urinalysis, and serology), and urine drug and alcohol screens will be collected at designated time points throughout the study. Subjects will be discharged from the clinic on Day 6, once all procedures are completed (or at Early Termination).


Number of Subjects (Planned):
 
An appropriate number of subjects will be randomized on Day 1 (Part A) to ensure that a minimum of 54 subjects complete the study. Replacement subjects may be enrolled to ensure that the minimum number of subjects complete the study.
 
Criteria for Inclusion/Exclusion:
 
Subjects will be required to meet each one of the following inclusion criteria in order to be eligible for participation in the study:
 
1. Must provide written informed consent prior to the initiation of any protocol-specific procedures.2. Male and female adults, between 22 to 65 years of age, inclusive.3. Body mass index (BMI) within 18.0 to 35.0 kg/m², inclusive (minimum weight of at least 50.0 kg at Screening).4. Healthy, as determined by no clinically significant medical history, physical examination, 12-lead ECG, vital signs or laboratory (including hematology, clinical chemistry, urinalysis, and serology) findings at Screening, as judged by an investigator.5. Smoking history of an average of at least 10 manufactured non-menthol flavored filtered standard (i.e., not slim) king size combustible cigarettes daily for at least 1 year prior to Screening. Brief

Name of Sponsor/Company: 22nd Century Group Inc.
 
Name of Finished Product: Very Low Nicotine (VLN) cigarettes (0.4 mg nicotine/gram of tobacco)


periods (i.e., up to 7 consecutive days) of non-smoking during the 3 months prior to Screening (e.g., due to illness or participation in a study where smoking was prohibited) will be permitted.
 
6. Self-reporting of desire to smoke within approximately 30 minutes of waking.
 
7. Positive urine cotinine (≥ 500 ng/mL) at Screening.
 
8. Negative pregnancy test at Screening and Day -1 (check-in) for all female subjects.
 
9. Female subjects of non-childbearing potential must be surgically sterile or 1 year postmenopausal (as confirmed by serum Follicle Stimulating Hormone [FSH] > 35 U/L). A subject is considered to be surgically sterile if she has had a tubal ligation, hysterectomy, bilateral salpingo-oophorectomy or bilateral oophorectomy, or hysterectomy with bilateral salpingo-oophorectomy. If the subject is of childbearing potential, she must be using a medically accepted method of contraception and agree to continued use of this method for the duration of the study and for 30 days after completion of the study. Acceptable methods of contraception include abstinence, birth control pill, or an intrauterine device (known to have a failure rate of less than 1% per year) or double barrier method of contraception (e.g., male condom in addition to a diaphragm, contraceptive sponge or spermicide).
 
10. Able to speak, read, and understand English sufficiently to allow completion of all study assessments.
 
11. Must be willing to comply with the requirements and restrictions of the study.
 
Subjects will not be eligible to participate in this study if any one of the following exclusion criteria is met:
 
1. Inability to tolerate 4 mg nicotine polacrilex gum during product use trial on Day -1 (check-in) or dentition prevents subjects from chewing gum.
 
2. History or presence of any clinically significant cardiac, psychiatric, endocrine, hematologic, hepatic, immunologic, metabolic, urologic, pulmonary, neurologic, dermatologic, renal, or other major disease at Screening, which in the opinion of an investigator would jeopardize the safety of the subject or the validity of the study results.
 
3. History or presence of any type of malignant tumors.
 
4. Clinically significant abnormal findings on the vital signs, physical examination (including oral exam), medical history, or clinical laboratory results, in the opinion of an investigator.
 
5. Positive serology test results for human immunodeficiency virus (HIV-1/HIV-2) Antibodies, hepatitis B surface antigen (HbsAg), or hepatitis C Antibody (HCVAb).
 
6. An acute illness (e.g., upper respiratory infection, viral infection) requiring treatment within 2 weeks prior to Day -1 (check-in).
 
7. Drug or alcohol abuse or dependence within the 24 months prior to Screening (except nicotine), as defined by the Diagnostic and Statistical Manual of Mental Disorders, 4th edition text revision (DSM-IV-TR), or any self-reported dependence or "addiction" within the subject's lifetime (except nicotine or caffeine).


Name of Sponsor/Company: 22nd Century Group Inc.
Name of Finished Product: Very Low Nicotine (VLN) cigarettes (0.4 mg nicotine/gram of tobacco)
8. Subjects who have ever been in treatment for substance use disorder(s) or who are currently seeking treatment for substance use disorder(s). 9. Positive urine drug screen (UDS) or urine alcohol test at Screening or Day -1 (check-in). 10. History or any current conditions that may interfere with drug absorption, distribution, metabolism, or excretion. 11. History of severe allergic reaction (including anaphylaxis) to any substance, or previous status asthmaticus, or food allergies/intolerances/restrictions, or special dietary needs which, in the judgment of an investigator, contraindicates the subject's participation in the study. 12. Requires concomitant treatment with prescription or non-prescription products that contain pseudoephedrine (e.g., nasal/sinus decongestants). 13. Self-reported use of nicotine polacrilex gum, or other nicotine replacement therapy products in the 30 days prior to Day -1 (check-in). Isolated incidents within 30 days prior to Day -1 (check-in) may be permitted at the discretion of the investigator. 14. Subject has unsuitable or difficult venous access or is unwilling or unable to undergo direct venipuncture or catheter insertion. 15. Subject has donated or lost 100 to 499 mL whole blood within 30 days or more than 499 mL whole blood within 56 days preceding entry into the Confined Assessment Phase. 16. Subject is an employee of the sponsor or research site personnel directly affiliated with this study or their immediate family member defined as a spouse, parent, child or sibling, whether biological or legally adopted. 17. Subject is lactating and or breast feeding. 18. A subject who, in the opinion of an investigator, is considered unsuitable or unlikely to comply with the study protocol for any reason.
Test Product: VLN cigarettes (0.4 mg nicotine/gram of tobacco)
Reference products: Own-brand non-menthol-flavored combustible cigarettes Nicorette® Original Flavor™ nicotine polacrilex gum (4 mg)
Duration of Study: Each subject will participate in the study for up to approximately five weeks, from Screening to Discharge.
Criteria for Evaluation: Pharmacodynamic Endpoints: The primary pharmacodynamic endpoints are: 
▪ Controlled Product Use (Part B):


Name of Sponsor/Company: 22nd Century Group Inc.
 
Name of Finished Product: Very Low Nicotine (VLN) cigarettes (0.4 mg nicotine/gram of tobacco)
 
○ $E_{max_urge(\text{controlled})}$: The maximum reduction in VAS score for the question “Urges to smoke” (Tobacco/Nicotine Withdrawal Questionnaire) between pre-use and post-use (i.e., $VAS_{\text{pre-use1}} - VAS_{\text{post-use1}}$) during the first product use in Part B.○ $E_{max_plst(\text{controlled})}$: The largest VAS score recorded for the response to the question “Is the product pleasant right now?” (Direct Effects of Product Questionnaire) during the first product use in Part B.

The secondary pharmacodynamic endpoints are:

Part A (Ad Libitum Product Use)
 
▪ Use the Product Again VAS score▪ Product use behavior (number of units consumed, duration of gum in mouth) 
Part B (Controlled and Uncontrolled Product Use)
 
▪ Tobacco/Nicotine Withdrawal Questionnaire:
○ $E_{max_item(\text{controlled})}$: The maximum reduction in VAS score for each item^a between pre-use and post-use (i.e., $VAS_{\text{pre-use1}} - VAS_{\text{post-use1}}$) during the first product use in Part B.○ $E_{max_item(\text{uncontrolled})}$: The maximum reduction in VAS score for each item between pre-use and post-use (i.e., $VAS_{\text{pre-use2}} - VAS_{\text{post-use2}}$) during the second product use in Part B.▪ Direct Effects of Product Questionnaire:
○ $E_{max_item(\text{controlled})}$: The largest VAS score recorded for the response to each item^b during the first product use in Part B.○ $E_{max_item(\text{uncontrolled})}$: The largest VAS score recorded for the response to each item during the second product use in Part B.▪ Product use behavior
○ Uncontrolled Product Use Sessions: number of inhalations, duration of inhalations [per puff], duration of polacrilex gum in mouth

Pharmacokinetic Endpoints:
 
▪ $C_{max(\text{controlled})}$: Maximum measured plasma nicotine concentration during the Controlled Use Session.▪ $C_{max(\text{uncontrolled})}$: Maximum measured plasma nicotine concentration during the Uncontrolled Use Session.▪ $AUC_{(\text{controlled})}$: Area under the nicotine concentration-time curve calculated using linear trapezoidal summation from time zero (defined as the start of controlled use) to 180 minutes (or the last quantifiable concentration during that interval).

^a Tobacco/Nicotine Withdrawal Questionnaire items (secondary): E_{max_urge} (uncontrolled only), E_{max_anx} , E_{max_dift} , E_{max_imp} , and E_{max_crav} .

^b Direct Effects of Product Questionnaire items (secondary): E_{max_plst} (uncontrolled only), E_{max_stf} , E_{max_calm} , E_{max_conc} , E_{max_awake} , E_{max_sick} , E_{max_hunger} , and E_{max_more} .

Name of Sponsor/Company: 22nd Century Group Inc.
 
Name of Finished Product: Very Low Nicotine (VLN) cigarettes (0.4 mg nicotine/gram of tobacco)
 
▪ $AUC_{(uncontrolled)}$: Area under the nicotine concentration-time curve calculated using linear trapezoidal summation from time 360 (defined as the start of uncontrolled use) to 540 minutes (or the last quantifiable concentration during that interval).▪ $T_{max\ (controlled)}$: Time of the maximum measured plasma nicotine concentration during the Controlled Use Session.▪ $T_{max(uncontrolled)}$: Time of the maximum measured plasma nicotine concentration during the Uncontrolled Use Session.▪ $Kel_{(controlled)}$: Apparent first-order terminal nicotine elimination rate constant calculated from a semi-log plot of the plasma concentration-time curve of the Controlled Use Session.▪ $Kel_{(uncontrolled)}$: Apparent first-order terminal nicotine elimination rate constant calculated from a semi-log plot of the Uncontrolled Use Session.▪ $T_{1/2\ (controlled)}$: Apparent first-order terminal nicotine elimination half-life calculated as $0.693/Kel$ of the plasma concentration-time curve from time zero (defined as the start of controlled use) to 180 minutes.▪ $T_{1/2(uncontrolled)}$: Apparent first-order terminal nicotine elimination half-life calculated as $0.693/Kel$ of the plasma concentration-time curve from time zero (defined as the start of uncontrolled use) to 540 minutes.

Safety:
 
The following safety endpoints will be evaluated:
 
▪ Incidence, frequency, severity, and relationship to product of AEs▪ Clinical laboratory assessments (hematology, biochemistry, urinalysis)▪ Vital signs (respiratory rate, pulse rate, blood pressure, and oral temperature)▪ 12-lead ECG▪ Physical examination results▪ Concomitant medications

Statistical Methods (Data Analysis):
 
Determination of Sample Size:
 
Using a 2-sided Type I error rate at $\alpha=0.05$ and assuming a mean difference in $E_{max_urge(controlled)}$ between own-brand cigarette and nicotine polacrilex gum of 15.85 points and standard deviation (SD) of 28.44, 54 completed subjects will be required to detect a significant difference between own-brand cigarette and nicotine polacrilex gum with greater than 80% power.
 
Using a 2-sided Type I error rate at $\alpha=0.05$ and assuming a mean difference in $E_{max_plst(controlled)}$ between own-brand cigarette and nicotine polacrilex gum of 35.21 points and SD of 31.82, estimate based on data obtained from the study site, 16 completed subjects will be adequate to detect a significant difference between own-brand cigarette and nicotine polacrilex gum with greater than 80% power.

Name of Sponsor/Company: 22nd Century Group Inc.

Name of Finished Product: Very Low Nicotine (VLN) cigarettes (0.4 mg nicotine/gram of tobacco)

The study analysis populations will be defined as follows:

Randomized Population (Part A): All subjects who are randomized into Part A.

Randomized Population (Part B): All subjects who are randomized into Part B.

Safety Population: All randomized subjects who use at least one of the study products. This will include Day -1 (check-in and product trial) and Study Days after the randomization. The Safety Population will be used for the summary of subject demographics, baseline characteristics, safety information, and AEs.

Pharmacodynamic Population: All subjects who use any study product and have pre-use (Tobacco/Nicotine Withdrawal questionnaire) and at least one post-use (for Tobacco/Nicotine Withdrawal and Direct Effects of Product) VAS score for the Controlled Use Session of Part B. This population will be used for statistical analyses of the pharmacodynamic measures.


PK Population: All subjects who use any study product and have pre- and at least one post-use plasma nicotine concentration value for the Controlled Use Session of Part B. The PK Population will be used for statistical analyses of the PK parameters.

Completer Population: All randomized subjects who complete all product use periods and have PK and pharmacodynamic data in the Controlled Use Session of Part B. This dataset will be used for analyses of the two primary pharmacodynamic measures endpoints as a sensitivity analysis to the primary analysis.

Pharmacodynamic Measures:

Part A:

Responses to Use the Product Again VAS will be summarized by study product using descriptive statistics. A summary table of frequencies will also be provided.

Product use behavior (number of units, duration of gum in mouth) will be summarized by study product using descriptive statistics.

Part B:

Responses to each Tobacco/Nicotine Withdrawal Questionnaire and Direct Effects of Product Questionnaire item will be summarized by time point for each study product, and product use condition. For Tobacco/Nicotine Withdrawal VAS scores, descriptive statistics for the difference from pre-use at each time point will also be reported. Derived parameters (E_{max}) for each questionnaire item will be summarized using descriptive statistics.

A linear mixed effects model for analysis of variance/covariance (Proc Mixed) will be performed on $E_{max_urge(controlled)}$ and $E_{max_plst(controlled)}$. The model will include E_{max} as the response variable, sequence, study product, and period as fixed model effects, baseline score as a covariate (for E_{max_urge} only) and subject nested-within sequence as a random effect. Sequence will be tested using subject nested-within-sequence as the error term. Least square mean (LSM) and 95% confidence interval (CI) for each Study Product group will be provided. Comparisons will be made for Product A vs. B, A vs. C and B vs. C. The comparison between Product A and Product C will be used as a comparison for internal validity. The LSM difference, p value and 95% CI of the difference will be provided.

Name of Sponsor/Company: 22nd Century Group Inc.

Name of Finished Product: Very Low Nicotine (VLN) cigarettes (0.4 mg nicotine/gram of tobacco)


The same model will be used for $E_{max_urge(uncontrolled)}$ and $E_{max_plst(uncontrolled)}$, and all E_{max} of other questions in the Tobacco/Nicotine Withdrawal Questionnaire and Direct Effects of Product Questionnaire for the controlled and uncontrolled product uses in Part B.

Product use behavior will be summarized by product using descriptive statistics.

Pharmacokinetics:
 
Descriptive statistics of plasma nicotine concentrations will be tabulated by time point for each study product and product use condition. Derived PK parameters (both unadjusted for baseline and baseline-adjusted) will be summarized using descriptive statistics. Summaries and individual data will be provided for plasma nicotine-adjusted concentrations.
 
A linear mixed model for analysis of variance (Proc Mixed) will be performed on the baseline-adjusted log transformed nicotine PK parameters in Part B. The model will include sequence, study product, and period as fixed effects and subject nested within sequence as a random effect. Sequence will be tested using subject nested-within sequence as the error term. From each model, the geometric LSM and 95% CI will be calculated for each study product. Separate analyses will be performed on the parameters calculated for the controlled and uncontrolled product use sessions. Geometric mean ratios for each pair comparison, 95% CI and p value will be provided.
 
The same linear mixed effect model as used for the analysis of $C_{max(controlled)}$ will be used for $C_{max(uncontrolled)}$ of second product use in Part B, and for AUC following all product uses. The Hodges-Lehmann's method will be used to estimate the median differences and the 95% CI of T_{max} and $T_{1/2}$ between the products.


Safety:
 
A by-subject AE data listing, including verbatim term, preferred term, study product, severity, and relationship to study product, will be provided. Study product use-emergent AEs will be summarized with tables. Frequencies of subjects with AEs, serious adverse events (SAEs) and incidence of those events, regardless of relationship to study product, will be summarized by study product and sorted by system organ class. Frequencies of AEs will be summarized by severity and relationship to study product. Clinical laboratory evaluations (serum chemistry, hematology, and urinalysis), vital signs measurements (blood pressure, pulse, respiration, and oral temperature) and ECG measurements (VR, PR, QRS, QT, and QTcF intervals) will be summarized descriptively. All concomitant medications recorded during the study will be listed by subject. Physical examinations will be listed by subject and time point of collection.

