5. INTRODUCTION

5.1. Background

With the introduction of the 2009 Family Smoking Prevention and Tobacco Control Act, the Food and Drug Administration (FDA) was granted the authority to regulate tobacco products including the nicotine content of cigarettes. In July 2017, FDA Commissioner [name]., announced the FDA's intention to limit nicotine in cigarettes to minimally or non-addictive levels. During his announcement, [name] stated that it has long been known that nicotine is the primary addictive component of cigarettes and that if smokers lose their addiction to cigarettes, they will be free to choose when and how often to smoke. A key component in the FDA's announced plan is to provide current smokers who are unable or unwilling to quit using nicotine with other, less harmful, means to obtain it. In other words, to provide a migration route away from traditional cigarettes to other types of tobacco or nicotine products such as cigarettes based on heat not burn technology, traditional smokeless, Snus, or electronic nicotine delivery system (ENDS) products.

Historically, tobacco harm reduction initiatives have focused on efforts to prevent or reduce tobacco initiation rates, increase quit rates, and decrease recidivism. The proposed reduction of nicotine cigarettes is believed to represent a viable policy tool to impact cigarette initiation rates and cigarette quit rates. Studies conducted to date indicate that reducing the nicotine content of cigarettes to non-addictive levels would potentially limit the reinforcing effects of cigarettes. A number of recent studies suggests that cigarettes with very low nicotine (VLN) content are associated with a positive set of outcomes, including reductions in the number of cigarettes smoked, reductions in nicotine exposure and nicotine dependence, increased abstinence from smoking, reduced exposure to toxicants, and fewer adverse events (AEs) (Rupprecht et al., 2017; Donny et al., 2007; Donny et al., 2015; Benowitz et al., 2007; Benowitz et al., 2009; Benowitz et al., 2012; Hatsukami et al., 2013). These studies evaluated cigarettes with nicotine content ranging from 0.4 to 15.8 mg nicotine per gram of tobacco with the typical combustible cigarette tobacco content ranging from approximately 8 mg to 20 mg.

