12.2. Determination of Sample Size

Sample size estimation was performed on both pharmacodynamic endpoints.

Using a 2-sided Type I error rate at $\alpha=0.05$ and assuming a mean difference in $E_{max_urge(\text{controlled})}$ between own-brand cigarette and nicotine polacrilex gum of 15.85 points and standard deviation (SD) of 28.44, 54 completed subjects will be required to detect a significant difference between own-brand cigarette and nicotine polacrilex gum with greater than 80% power.

Using a 2-sided Type I error rate at $\alpha=0.05$ and assuming a mean difference in $E_{max_plst(\text{controlled})}$ between own-brand cigarette and nicotine polacrilex gum of 35.21 points and SD of 31.82, estimate based on data obtained from the study site, 16 completed subjects will be adequate to detect a significant difference between own-brand cigarette and nicotine polacrilex gum with greater than 80% power.

An appropriate number of subjects will be randomized on Day 1 (Part A) to ensure that a minimum of 54 subjects complete the study. Replacement subjects may be enrolled to ensure that the minimum number of subjects complete the study.

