#### Statistical Analysis of PK Parameters

A linear mixed model for analysis of variance (Proc Mixed) will be performed on the baseline-adjusted log transformed nicotine PK parameters in Part B ( $C_{\text{max}}(\text{controlled})$ ,  $C_{\text{max}}(\text{uncontrolled})$ ,  $AUC_{(\text{controlled})}$  and  $AUC_{(\text{controlled})}$ ). The model will include sequence, study product, and period as fixed effects and subject nested-within sequence as a random effect. Sequence will be tested using subject nested-within sequence as the error term. From each model, the geometric LSM and 95% confidence intervals will be calculated for each study product. Separate analyses will be performed on the parameters calculated for the Controlled and Uncontrolled Use sessions. Geometric mean ratios for each pair comparison, 95% confidence interval and p value will be provided.

The SAS codes for the model will be as follows:

```
Proc MIXED data=test;
  class subject sequence period product;
  model log(Cmax0_180) = sequence period product / ddfm=KR;
  random subject (sequence) / type=UN;
  estimate "Product A vs Product B" product 1 -1 0 /cl alpha=0.05;
  estimate "Product A vs Product C" product 1 0 -1 /cl alpha=0.05;
  estimate "Product B vs Product C" product 0 1 -1 /cl alpha=0.05;
  lsmeans product/cl alpha=0.05;
run;
```

The Hodges-Lehmann's method will be used to estimate the median differences and the 95% confidence interval of  $T_{\text{max}}$  and  $T_{1/2}$  between the products for controlled and uncontrolled use.

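### The Part B mixed models give three very different products one residual variance, so the pairwise intervals may be too narrow or too wide; an unstructured within-subject covariance by product would remove the assumption at little cost

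*Protocol*

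**What the plan says.** The Protocol synopsis and section 12.4.3.2 define the Part B model for the Emax endpoints by its fixed effects (with a baseline covariate where one exists) "and subject nested-within sequence as a random effect. Sequence will be tested using subject nested-within-sequence as the error term". For log-transformed, baseline-adjusted PK, the synopsis states: "The model will include sequence, study product, and period as fixed effects and subject nested within sequence as a random effect". Section 12.4.4 and SAP section 9 repeat this: "The model will include sequence, study product, and period as fixed effects and subject nested-within sequence as a random effect".

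The SAP code for both models has one RANDOM statement for subject within sequence and no REPEATED statement or GROUP= option. The comparisons A vs B, A vs C and B vs C (A = VLN, B = own-brand, C = gum) all come from that one fit. The only sensitivity analysis for the primary endpoints changes the population (Completers), not the covariance.

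The products differ in kind. The synopsis lists "Product B: Own-brand non-menthol filtered standard king size cigarette", and Protocol 9.2 has each subject bring his or her own packs. VLN and the 4 mg gum are each one standard product. VLN tobacco has 0.4 mg nicotine per gram; Protocol 5.1 gives the "typical combustible cigarette tobacco content ranging from approximately 8 mg to 20 mg".

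**The concern.** A single random intercept is compound symmetry: equal variances for A, B and C and equal correlation for every pair. One pooled residual then serves all three contrasts. If one product is noisier than another, the pooled standard error is too small for some contrasts and too large for others.

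Equality is doubtful here. Own-brand can carry brand-to-brand differences that the two standard products do not. If Protocol 5.1 is read as milligrams per gram, VLN has 0.4/20 = 2% to 0.4/8 = 5% of typical nicotine content, so baseline-adjusted VLN concentrations should be low, and low values can scatter widely on a log scale. The VAS endpoints are bounded at 0 and 100, and large mean differences on a bounded scale also make equal spread questionable.

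At stake are the intervals and p-values for both primary endpoints, the secondary Emax items and the PK ratios.

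**Working it through.** **The plan's own figure.** Protocol 12.2 assumes, for urge, a difference "of 15.85 points and standard deviation (SD) of 28.44, 54 completed subjects will be required", "with greater than 80% power". If the SD is per product with no within-subject correlation, n = 2 × [28.44 × (1.960 + 0.842)/15.85]² = 50.5, so 51. With t critical values the minimum is 52 to 53, and power at 54 is 81.1% to 81.9%. For pleasantness (35.21, SD 31.82) the minimum is 14 to 15 against a stated 16, with power at 16 of 83.3% to 85.7%. Both stated numbers reproduce. If the SD were that of the paired difference, the t-based numbers would be 28 and 9, which do not match. Each calculation uses one SD, so section 12.2 says nothing about variances by product.

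**Closed form.** Take N = 54 complete subjects, 18 per sequence (ABC, BCA, CAB), and residual variances vA, vB, vC around the subject effect.

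- Variance used by the planned model for every contrast: (2/3)(vA + vB + vC)/N, on 162 − 54 − 2 − 2 = 104 df.
- True variance of A−B: (vA + vB)/N.
- Ratio of planned to true SE for A−B: √[(2/3)(vA + vB + vC)/(vA + vB)].
- This ratio is below 1 only when (vA + vB)/2 > vC. The same rule holds for the other contrasts with the letters exchanged.

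Examples: variances (1, 2, 1) give √[(2/3)(4/3)] = 0.94; (1, 1, 2) give √[(2/3)(4/2)] = 1.15.

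**Simulated coverage of the planned 95% intervals** (20,000 trials per row, no covariate; the relative variances are assumptions):

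| vA, vB, vC (VLN, own-brand, gum) | SE ratio A−B | A−B | A−C | B−C |
|---|---|---|---|---|
| 1, 1, 1 | 1.00 | 95.0% | 95.1% | 95.1% |
| 1, 2, 1 | 0.94 | 93.8% | 97.7% | 93.8% |
| 1, 4, 1 | 0.89 | 92.3% | 99.4% | 92.3% |
| 2, 1, 1 | 0.94 | 93.9% | 93.8% | 97.7% |
| 2, 2, 1 | 0.91 | 93.0% | 96.2% | 96.3% |
| 0.5, 1.5, 1 | 1.00 | 95.3% | 97.8% | 92.3% |
| 0.25, 1, 1 | 1.10 | 96.9% | 97.1% | 91.4% |
| 0.5, 2, 2 | 1.10 | 96.8% | 96.7% | 91.0% |
| 1, 1, 2 | 1.15 | 97.8% | 93.8% | 93.7% |

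A gum variance four times the others gave 99.5% for A−B in a further run. Intervals built from each contrast's own within-sequence variance (54 − 3 = 51 df) covered 94.5% to 95.2% throughout. Fitting the unstructured 3x3 model itself to complete data, with and without a baseline covariate, gave about 94% to 96%.

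**On the VAS scale.** If the average residual SD is 28.44 (an assumption), the planned half-width for A−B is 1.98 × 28.44 × √(2/54) ≈ 10.9 points. At the same average variance, the contrast-specific half-width is 11.7 for (1, 2, 1), 12.3 for (1, 4, 1), 10.0 for (0.25, 1, 1) and 9.5 for (0.5, 1, 1.5).

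**Cost under equal variances.** The half-width goes from 10.86 to 10.99, a factor of 1.012.

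**The case against.** A random subject effect is a conventional crossover model, and no document shows that the variances differ. The reasons for expecting inequality also have counterparts. Protocol 7.2 expects own-brand to be the most reinforcing product, so its ratings could cluster near the top of the scale and be the least variable. Gum is unfamiliar (recent use is generally excluded, and subjects must be trained on it), so its ratings could be the most variable. The low-nicotine argument applies to PK, a secondary objective, and not directly to the two VAS endpoints. All of this stands, and it leaves the direction open.

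A reader might infer that the VLN versus own-brand interval is likely too narrow. The documents do not support that. It requires the average VLN and own-brand variance to exceed the gum variance, and gum's variance is as unknown as the others. A quiet VLN or a noisy gum makes the interval too wide, and the effects can cancel. Nor do the documents show that VLN values lie at the assay limit, since neither states one.

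Two possible defences fail. `type=UN` on a single random intercept is one scalar, so it does not free the variances by product. `ddfm=KR` adjusts the standard errors and df under the assumed structure and does not relax it. The per-product Emax SDs to be tabulated would show unequal spread but would not correct the intervals.

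It is also fair to say that the remedy costs more than a few df: the contrasts fall from 104 to about 51. The coverage results are for complete data; missing periods and the fallback structure were not tested.

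**Conclusion.** The concern holds without a direction. The planned models impose equal variances and correlations on three unlike products, and nothing in either document relaxes or tests this. For assumed variances 2- to 4-fold apart, coverage of individual contrasts runs from about 91% to over 99%; for A−B alone the error can go either way.

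One consequence follows from the algebra: if VLN is the least variable product, B−C, the own-brand versus gum comparison that the sample size rests on, is necessarily too narrow (90% to 92% coverage in the simulated cases).

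The size is modest, about one VAS point of half-width in most of the cases shown, and it rests on assumed variance ratios. The concern is most plausible for log baseline-adjusted PK. Because the remedy is cheap and best fixed before the data are seen, this is a worthwhile improvement rather than a fatal defect.

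**What to change.** In the Protocol synopsis, Protocol 12.4.3.2 and 12.4.4, and SAP section 9 (both PD and PK models), replace the random intercept with an unstructured 3x3 within-subject covariance by product: `repeated product / subject=subject(sequence) type=UN`, keeping `ddfm=KR`. Name heterogeneous compound symmetry (`type=CSH`) as the fallback if the fit does not converge. Keep the fixed effects and the three named comparisons. The sentence that tests sequence against subject within sequence must change too: test sequence with the Kenward-Roger df from the same model.

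The cost is about half the denominator df for the contrasts (104 to about 51). If variances are equal, intervals are about 1% wider without a covariate and possibly a few percent more with a baseline covariate (about 7% in one simulated set-up). The notes under table shells 14.2.2.1.1, 14.2.3.3.1.1 and 14.2.3.3.1.4 need matching edits.

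Separately, the SAP's PD code labels one estimate as A vs B but gives it the coefficients 1 0 −1, which is A vs C. That needs its own correction; this change does not repair it.
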